Statistical analysis and calculation of number of patients	The objective of this study is to demonstrate an improvement of the overall survival in patients with a donor that is reaching 70% at 36 months compared to 40% in those without a donor. To test this hypothesis (HR=0.39) based on a two-sided log-rank test, 50 events are required, and 105 patients are needed with a 80% power and type I error rate at 5%, with a probability to identify a donor at 70%								
Study duration	Patient recruitment: 36 months Minimal Patient follow-up: 24 months and until the end of the trial scheduled 60 months after first inclusion (approximately June 2021) Total duration of the study: 60 months								
Number of centers	20-25								
Administration and authorities	CNIL ANSM CPP Clinicaltrials.gov								

List of abbreviations

AE	Adverse Event
ANC	Absolute Neutrophil Count
ANSM	Agence nationale de sécurité du médicament et des produits de santé
AML	Acute Myeloid Leukemia
ALT	Alanine Aminotransferase (or Serum Glutamate-Pyruvate Transaminase)
АР	Alkaline Phosphatase
AST	Aspartate Aminotransferase (or Serum Glutamate-Oxylate Transaminase)
ATG	Antithymoglobulin
BM	Bone Marrow
CBC	Complete Blood Count
CI	Coordinating Investigator
CMML	Chronic Myelomonocytic Leukemia
CMV	Cytomegalovirus
СРК	Serum creatine phosphokinase
СРР	Comité de Protection des Personnes
CR	Complete Remission
CRA	Clinical Research Assistant
CRF	Case Report Form
CTCAE	Common Terminology Criteria for Adverse Events
d	Day
DSMB	Data and Safety Monitoring Board
EBV	Epstein Barr Virus
ECG	Electrocardiogram
ECOG	Eastern Cooperative Oncology Group
ESA	Erythropoiesis stimulating agents
FAB	French-American-British
GCP	Good Clinical Practice
G-CSF	Granulocyte-colony stimulating factor
GFM	Groupe Francophone des Myélodysplasies
GVHD	Graft-versus-host disease
HLA	Human leucocytes antigens
h UCV	Hour Hourthin Chima
HCV	Hepatitis C Virus
HSCT	Hematopoietic Stem Cell transplant
IPSS LDH	International Prognostic Scoring System
	Lactate Dehydrogenase Liver iron content
MAC	Myelo-ablative conditioning regimen
MDS	Myelodysplastic Syndrome
NRM	Non relapse mortality
NTBI	Non-transferin-bound iron
OS	Overall Survival
PS	Performance Status
RBC	Red Blood Cell
RCT	Randomized Controlled Trial
REB	Research Ethics Board
RIC	Reduced intensity conditioning regimen
SAE	Serious Adverse Event
SGOT	Serum Glutamate-Oxalate Transferase (or Aspartate Aminotransferase)
SGPT	Serum Glutamate-Pyruvate Transferase (or Alanine Aminotransferase)

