3.2 Secondary Objectives

- ✓ Comparison between patients with or without a donor for:
 - a. Cumulative incidence of complete response at 36 months
 - b. Cumulative incidence of Transformation in AML at 36 months (according to WHO criteria, > 20% blasts in peripheral blood or bone marrow)

Evaluate:

- ✓ Risk factors for outcome (remission, mortality)
- Risk factors for overall survival (age, disease characteristics...) including iron overload (ferritin, plasmatic iron markers, MRI)
- ✓ The efficiency of chelation will be assessed at 3 months after inclusion for all patients
- ✓ Feasibility of the transplant define by the proportion of patients with a donor who undergo the transplantation (expected between 80 and 95%)
- ✓ Proportion of patients with iron overload (Serum Ferritin (SF) > 1000 ng/mL or RBC transfusion > 20) at time of inclusion and at 16 months after inclusion for non-transplanted patients and 12 months post-transplant for transplanted patients
- ✓ The effect of chelation post-transplant will be measured by SF level: SF < 1000 ng/mL, SF > 1000 ng/mL, SF > 1500 ng/mL and also by percentage of patients with SF decrease of at least 30%
- Eligibility of post-transplant Exjade[®] treatment defined by the proportion of patients with iron overload who can benefit from Exjade[®] after the transplantation (% of patients without contraindication to Exjade[®] 3 months after transplant) and who can maintained it at least 6 months or until SF < 700 ng/mL
- ✓ Assessment of change of Ferritin level (% of decrease) and MRI at 12 months post-transplant
- Evolution of innovative iron markers including Non-transferrin binding iron (NTBI), labile plasmatic Iron (LPI) and Hepcidine at time of inclusion (before Exjade®), at 3 months (patients potentially treated by Exjade®) and 16 months post-inclusion for all patients; in transplanted patients these markers will be measured just before conditioning regimen (J-5), just before the transplantation (J0), at D7, 30, 100 and 12 months after transplant. All these markers will be tested as risk factors for outcome (survival, non-relapse mortality and progressive disease)
- ✓ Quality of Life study (EORTC questionnaire at registration, 12, 24 and 36 months)
- ✓ Grade III or IV toxicity (hematological and non-hematological) recorded according to NCI CTC criteria version 4.0
- ✓ Cumulative incidence of severe infection at 12 months

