4.3. Discontinuation criteria

All patients will be followed at least 2 years after the date of the last inclusion according to each center policy and disease status (transformation in a higher risk MDS, especially AML) and death (date and cause) will be collected until the end of the protocol and for a maximal duration of 5 years.

5. Number of patients and study duration

- The trial will enroll **105** patients, 62 in group A (donor), 43 in group B (no donor), over a 36-month period
- The whole study will be performed over a 5-year period

6. Therapeutic procedures

Patients will be assigned to group A or B (donor or no donor) after at least 2 months after inclusion to allow the time for donor search.

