9.3. Statistical analysis

All analyses will be performed in an intent-to-treat approach, whatever the treatment actually performed (either transplantation or not); the basis for comparison will indeed be the selection of a donor or not. Such a design is often considered as a "Mendelian randomization". Mendelian randomization is a method that allows one to test for, or in certain cases to estimate, a causal effect from observational data in the presence of confounding factors⁹⁰. From a statistical perspective, it is an application of the technique of instrumental variables⁹¹, with genotype acting as an instrument for the exposure of interest. However, Mendelian randomization estimates are especially relevant when the effect of interest is that of a long term population based intervention. Otherwise, a Mendelian randomization approach will generally be qualitatively informative for the direction of effect of a clinical intervention, the genetically derived estimate might not correspond to the magnitude of the effect in practice. Thus, two analyses will be conducted, with two main estimates of intervention effect:

- directly comparing those two groups (donor vs no donor)
- using inverse probability treatment weights, based on the propensity scores to have actually a donor.

Baseline characteristics, overall and complete response rates of the two groups will be compared by nonparametric tests, either the exact Fisher's exact test for qualitative variables or the Mann-Whitney test for quantitative variables. Cumulative incidences of AML will be tested with the Gray test considered death as a competitive event. Prognostic factors of event-free and overall survival will be investigated using Cox proportional hazard models. Model assumptions will be checked using a test for proportional hazards and spline smoothing of residuals for the log-linearity assumption.

All statistical analyses will be performed with the R and SAS software packages.

10. Safety assessment

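### Complete response is defined as a 36-month cumulative incidence, but section 9.3 compares crude response rates with Fisher's exact test and sets no time window, although follow-up runs from 24 to 60 months

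*Protocol*

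**What the plan says.** Protocol section 3.2 lists two donor versus no-donor comparisons with the same horizon: "Cumulative incidence of complete response at 36 months" and "Cumulative incidence of Transformation in AML at 36 months".

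Section 9.3 handles them differently. AML gets a competing-risks method: "Cumulative incidences of AML will be tested with the Gray test considered death as a competitive event". CR is placed in the sentence on baseline characteristics, where "overall and complete response rates of the two groups will be compared by nonparametric tests", the tests being "either the exact Fisher's exact test for qualitative variables or the Mann-Whitney test for quantitative variables". CR as a yes/no variable is qualitative, so Fisher's exact test applies. Section 9.3 does not say by what time a response must occur to count, and it names no cumulative-incidence estimate or test for CR.

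The protocol synopsis fixes the follow-up: "Patient recruitment: 36 months", with a minimum follow-up of "24 months and until the end of the trial scheduled 60 months after first inclusion". Section 5 gives the group sizes: "62 in group A (donor), 43 in group B (no donor").

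**The concern.** The two objectives are defined alike, yet only AML has an analysis that matches its definition. A proportion of responders equals a 36-month cumulative incidence only if everyone is observed to month 36 and later responses are ignored. Here late entrants can leave observation from month 24 and early entrants stay until month 60.

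At stake is whether the reported CR figure is the one that the objective names. An SAP that follows section 9.3 would not deliver the objective in section 3.2, and an SAP that delivers the objective would depart from section 9.3. The rate also depends on how long patients survive under observation. Two groups with the same 36-month incidence can therefore show different crude rates because one of them lives longer.

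**Working it through.** The protocol states no CR rate, power or sample size for CR, so there is no CR figure of its own to reproduce.

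**Inputs from the protocol.** Accrual 36 months; end at 60 months; 62 donor (A) and 43 no-donor (B) patients; planned 36-month survival 70% and 40% (section 9.1).

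**Assumptions.** Uniform accrual, so potential follow-up is uniform on 24 to 60 months; constant hazards of CR and death; CR levels chosen to span a range.

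**1. Potential follow-up under 36 months.** (36 − 24)/(60 − 24) = 12/36 = 33%, or 35 of 105 patients.

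**2. Alive and censored before month 36.** The monthly death hazard is λ = −ln(S)/36: 0.00991 in A (S = 0.70) and 0.02545 in B (S = 0.40). The share alive at a cut-off between months 24 and 36 is

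(1/3) × [exp(−24λ) − exp(−36λ)]/(12λ)

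- A: 24.8%, or 15.4 of 62 patients
- B: 15.6%, or 6.7 of 43 patients
- Together: 22.1 of 105, or 21%

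Patients already in CR are not censored for CR. With a CR hazard h of 0.003 to 0.02 per month (replace λ by h + λ), the number censored with neither event falls to between 20.2 (14.05 + 6.13) and 12.2 (8.47 + 3.71) of 105, about 19% to 12%.

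**3. Crude rate against the 36-month incidence.** The cumulative incidence at time t is h/(h + λ) × [1 − exp(−(h + λ)t)]. The crude rate over all follow-up averages this over t uniform on 24 to 60 months. The crude rate limited to month 36, with censored patients as non-responders, is (1/3) × its mean over 24 to 36 months + (2/3) × its value at 36 months.

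| True 36-month CR | Group | Crude, by month 36 | Crude, all follow-up |
|---|---|---|---|
| 10% | A | 9.5% | 11.1% |
| 10% | B | 9.7% | 10.6% |
| 20% | A | 19.1% | 21.9% |
| 20% | B | 19.4% | 21.1% |
| 40% | A | 38.5% | 42.8% |
| 40% | B | 39.0% | 41.3% |
| 60% | A | 58.3% | 62.5% |
| 60% | B | 59.1% | 60.7% |

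With one CR hazard of 0.02 per month in both groups, the 36-month incidence and the crude all-follow-up rate are 44.1% and 46.9% in A, and 35.4% and 36.7% in B. At the low end (h = 0.003, group B, responses by month 36) the error is 0.24 points. The errors thus run from about 0.2 to 3 points.

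**4. Effect on the group contrast.** With a true 40% in both groups, the all-follow-up rates differ by 42.8 − 41.3 = 1.5 points. The standard error of a difference near 40% is √(0.4 × 0.6/62 + 0.4 × 0.6/43) = 9.7 points.

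**5. Error rates.** Simulation with 2,000 runs, 62 versus 43 patients, responses counted to month 36, against a Gray-type subdistribution log-rank test:

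| 36-month CR, A vs B | Fisher rejects | Gray-type rejects |
|---|---|---|
| 20% vs 20% | 3.5% | 5.3% |
| 40% vs 40% | 3.9% | 5.8% |
| 40% vs 15% | 73.5% | 77.1% |
| 50% vs 25% | 70.3% | 70.9% |

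**The case against.** The case for leaving the text alone has four parts.

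- **The numbers barely move.** A contrast shift of about 1.5 points is small beside a standard error of 9.7 points, Fisher's test does not reject too often, and the power gain is 0.6 to 3.6 points. If donor patients reach CR soon after a transplant scheduled 4 months after inclusion (section 6.1), most of their responses fall inside everyone's 24-month minimum and the bias shrinks further. This stands. It limits the urgency but does not make the rate the stated endpoint.
- **The timing of CR is recorded unevenly.** CR needs a marrow result (Appendix 8). Transplanted patients have a marrow between days 60 and 100, while others may have one only yearly (section 8 diary, note 5). A test that uses timing will pick up part of that difference. This stands and shapes the fix.
- **Gray's test compares whole curves.** Without truncation it too would use responses after month 36. This also stands, and truncation answers it.
- **The sentence may describe best-response rates only**, since it pairs CR with overall response, which is not among the comparisons in section 3.2, and the 36-month estimate may be left to the SAP. That is possible, but section 9.3 gives this as its only between-group analysis of CR, so a method is stated and it does not fit the objective.

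A reader might also infer that Fisher's test mishandles death. It does not: patients who die without CR stay in the denominator as non-responders, just as in a cumulative incidence with death competing, and with complete 36-month follow-up the two are equal. Only administrative censoring and the missing time window separate them.

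**Conclusion.** Sections 3.2 and 9.3 do not agree on CR. As written, the analysis does not estimate the 36-month cumulative incidence, and it should be corrected. The error is about 0.2 to 3 percentage points in a group's CR figure, given uniform accrual, constant hazards and the planned survival rates; it is smaller if CR comes early. The CR levels are assumptions, because the protocol gives none. CR is a secondary endpoint and the primary survival conclusion is unaffected.

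Two stronger readings are not supported. First, one third of patients are not censored before month 36: one third have a potential follow-up shorter than that, and about 21% would be alive and censored. Second, a reader might extend the point to severe infection, engraftment, GVHD or non-relapse mortality. Section 9.3 states no wrong test for these. Infection at 12 months and engraftment at day 60 also have horizons inside the 24-month minimum follow-up.

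**What to change.** In section 9.3, take CR out of the sentence on Fisher's test and add, for example: *The cumulative incidence of complete response will be estimated by group with the Aalen-Johansen estimator, with death without complete response as a competing event, and reported at 36 months with a 95% confidence interval. Groups will be compared with Gray's test on follow-up truncated at 36 months.* Keep Fisher's test for baseline characteristics. If overall and best-response rates are still wanted, label them descriptive and give their time window.

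State that the 36-month estimate is the main CR result and that the comparison of timing is read with caution, because marrow schedules differ by group.

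The cost is two or three sentences. No extra data are needed, and the protocol already uses Gray's test with death competing for AML. The one drawback is the greater exposure to assessment timing, which the emphasis on the 36-month estimate contains.

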10.1. Assessment of adverse events (AE)

Safety will be assessed continuously during the study. Patients should be questioned at each scheduled visit concerning AEs experienced since last visit. The severity, as graded by the NCI CTC AE v. 4.0 (Cf. Appendix 9), date of onset, and outcome should be recorded for all AEs as well action taken (such as prescription of rescue medication). All concomitant medication taken by the patient will be collected. An adverse event (AE) is defined as any expected or unexpected harmful and unintended occurrence or exacerbation of an event in a clinical trial subject, whether or not related to the trial or the investigational product. It can be a new intercurrent disease, exacerbation of a concomitant disease, an accident, or any other deterioration in the patient's health, including abnormal laboratory findings.

Any medical condition that existed before the start of the study treatment and that remains unchanged or improves must not be recorded as an AE. If a medical condition worsens, it must be recorded as an AE. The diagnosis or syndrome rather than the individual signs or symptoms must be recorded on the AE pages of the case report form. An adverse reaction is any untoward and unintended responses to an investigational medicinal product related to any dose administered.

10.2. Assessment of serious adverse events

An event is considered a serious adverse event (SAE) if it:

- Results in death
- Is life-threatening
- Requires inpatient hospitalization (except for the transplantation) or prolongation of existing hospitalization (expect hospitalization for transplant)
- > Causes permanent disability or serious temporary incapacity
- Causes a congenital anomaly, birth defect or abortion
- Is medically significant

The terms disability and incapacity refer to any clinically significant physical or mental handicap, whether temporary or permanent, that affects the patient's physical activity and/or quality of life.

A medically significant event is any clinical event or laboratory finding considered by the investigator to be serious that does not meet the seriousness criteria defined above. It may pose a risk to the patient and require medical intervention to prevent one of the serious outcomes mentioned previously (e.g. an overdose, second cancer, pregnancy, and new information can be considered medically significant).

The following are not considered as serious adverse events:

- Hospitalization scheduled before the start of the trial and/or stipulated in the protocol (e.g. for biopsy or chemotherapy) or for social reasons
- > Aplasia related to conditioning regimen
- Transfusions

The AE pages of the case report form and an SAE form should be completed for each AE considered serious.

For each AE, the investigator shall provide information about the intensity, start and end dates, causality, the action taken, and the outcome.

Definition of an expected serious adverse event (SAE-E)

An expected SAE is an event already mentioned in the most recent version of the Investigator Brochure, or in the Summary of Product Characteristics (SmPC) for medicinal products that have already been granted marketing authorization (MA). This definition also applies to the trial drug when it is administered for the same population but for an unlicensed indication.

Definition of an unexpected serious adverse event (SAE-U)

An unexpected SAE is an event not mentioned in or whose nature, intensity, or clinical course is not consistent with the information in the Investigator Brochure, or in the Summary of Product Characteristics (SmPC) for medicinal products that have already been granted marketing authorization (MA).

Intensity

The term intensity (severity) should not be confused with the term seriousness that serves as a guide for defining reporting obligations.

The intensity of events shall be evaluated according to the excerpt from the CTC-AE classification, version 4.0 (cf. Appendix 9). The intensity of adverse events not listed in this classification will be rated using the following terms:

- > Mild (grade 1): does not affect the patient's usual daily activities
- Moderate (grade 2): interferes with the patient's usual daily activities
- Severe (grade 3): prevents the patient's usual daily activities
- Very severe (grade 4): requires intensive care / is life-threatening
- Death (grade 5)

Causal relationship between an adverse event (SAE/AE) and the study treatment

The investigator must determine the cause-effect relationship between administration of the treatment and the incidence of an adverse event (SAE/AE), and rate it as Suspected or Not Suspected, as follows:

Not Suspected:

The timing makes a causal link between the adverse event and administration of the study drug unlikely, or alternatively the concomitant administration of other medicinal products or therapeutic interventions or preexisting disorders provide sufficient explanation for the observed event.

Suspected:

The timing makes a causal link between the adverse event and administration of the study drug possible, and concomitant administration of other medicinal products, therapeutic interventions and pre-existing disorders do not sufficiently explain the observed event.

10.3. Reporting of SAEs

The investigator must report any SAE that occurs during the study regardless the causality of the event is related or not to the study drug, to the principal investigator and the sponsor, by fax or e-mail. The investigator must complete and send the serious adverse event report form within 24 hours of learning of the serious event to:

GFM
[name]
Service d'Hématologie Séniors
Hôpital Saint-Iouis
[name]
[name]
[contact]
[contact]
[contact]

The sponsor shall provide NEOVII a copy of all expected or unexpected serious adverse events within 24 hours of learning of the event.

The sponsor shall also provide NEOVII a copy of the annual safety report at the time of its submission to the REB and the regulatory authorities.

QPPV Name: [name] [name]

Protocole version 4 du 06-10-2017

Address: YES Pharma Services GmbH [name] Germany Email: [contact]

Deputy QPPV Name: [name] [name] Address: Neovii Biotech GmbH [name] Germany Phone (24 h): [name] [contact] Email: [contact]

The sponsor shall provide NOVARTIS a copy of all expected or unexpected serious adverse events within 15 days of learning of the event by email to: https://www.novartis.com

The sponsor shall also provide NOVARTIS a copy of the annual safety report at the time of its submission to the REB and the regulatory authorities.

Reporting period

All SAEs must be reported:

- Since the signing of consent,
- Up to 30 days following the transplant or following the last study drug therapy

Any delayed serious adverse event that may reasonably be considered related to the treatment(s) described in the protocol or to the study must be reported, and no time limit applies to such adverse events.

For each event, the investigator shall record:

- A description of the event that is as clear as possible, using medical terminology,
- Its intensity,
- Its start and end dates,
- The measures taken and whether or not corrective treatment was required,
- Whether the trial treatment was suspended,
- Its clinical course. If the event was not fatal, it should be monitored until recovery, until the patient has
 returned to his/her previous condition, or until any sequelae have stabilized,
- The causal relationship between the event and the trial treatment or any trial-related obligations (e.g. a treatment-free period, investigations requested in connection with the trial),

Any causal link with the trial medication(s), the disorder being treated, another disorder or another treatment. Whenever possible, the investigator must also send the following with the serious adverse event report: a copy of the discharge summary for hospitalization or prolonged hospitalization, a copy of the post-mortem report, a copy of all the results of the diagnostic tests performed, including relevant negative results, together with the normal laboratory values, and any other documents the investigator considers useful and relevant.

All of these documents must be anonymized.

Additional information may be requested by the monitor (by fax, post, telephone, or during a visit).

Nevertheless, any event that qualifies as expected but differs in its intensity, clinical course, or frequency will be considered as an unexpected event by the Pharmacovigilance unit.

Reporting events to the Authorities and the REB

The sponsor shall report the following to the French health products safety agency (ANSM) and the REB concerned:

- Unexpected serious adverse effects that might be related to the investigational product and resulted in death or were life-threatening, at once and within a maximum of seven days from the day the sponsor learned of the event. Additional relevant information shall be reported within a new time limit of eight days following on from the seven-day deadline.

- Other expected serious adverse effects that could be related to the investigational product, at once and within a maximum of fifteen days from the day the sponsor learned of the event. Additional relevant information shall be sent within a new time limit of eight days following on from this fifteen-day deadline.

Follow-up of SAEs

The investigator is responsible for providing appropriate medical follow-up for patients until the event has resolved or stabilized or until the patient's death. Sometimes this may mean that follow-up will extend beyond the patient's withdrawal from the trial.

The investigator shall send additional information to the sponsor using an SAE report form (ticking the box "Follow-up No. X" to specify that this is a follow-up report and not an initial report) within 48 hours of receiving the information. The investigator also sends the final follow-up once the SAE has resolved or stabilized.

The investigator shall keep the documents about the presumed adverse effect, in case anything needs to be added to the information previously sent.

The investigator shall respond to the sponsor's requests for additional information in order to document the initial report.

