The sponsor must be established in the European Community or, failing that, have a legal representative in a member state.

The sponsor's main responsibilities are to:

- take out civil liability insurance,
- request the opinion of the REB on the initial project and substantial amendments,
- request authorization for the initial project and substantial amendments from the competent authority,
- provide information about the trial to the site directors, investigators, and pharmacists,

- report any suspected unexpected serious adverse events related to any of the trial treatments to the competent authority, ANSM and EMEA (European pharmacovigilance database, Eudravigilance), and send this information to the REB and the trial investigators,

- submit the annual safety report to the competent authority and the REB,
- notify the competent authority of the start and end of the trial,
- write the final clinical study report,
- send the trial results to the competent authority, REB, and trial subjects,

- archive essential trial documents in the sponsor's folder for a minimum of 15 years after the trial has ended.

Responsibilities of investigators

The principal investigator of each establishment concerned undertakes to conduct the clinical trial in accordance with the protocol approved by the REB and the competent authority.

The investigator must not make any changes to the protocol without the written authorization of the sponsor and unless the REB and the competent authority have approved the proposed changes.

It is the responsibility of the principal investigator to:

- provide the sponsor with his/her curriculum vitae as well as those of his/her co-investigators,

- identify the members of his/her team who are participating in the trial and define their responsibilities,

- recruit patients once authorized to do so by the sponsor.

It is the responsibility of each investigator to:

- obtain informed consent, personally signed and dated by the subject, before carrying out any trial-specific screening procedures,

- regularly complete the case report form (CRF) of each patient enrolled in the trial and allow the clinical research assistant (CRA) appointed by the sponsor to have direct access to source documents, so that the latter can validate the data on the CRF,

- date, correct, and sign corrections on the CRF of each patient enrolled in the trial,

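### The 15-day authority-reporting rule names expected instead of unexpected reactions, so unexpected related serious reactions that are neither fatal nor life-threatening have no deadline

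*Protocol*

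**What the plan says.** Section 10.3 of the Protocol, under the heading on reporting to the authorities and the REB, sets two rules for the sponsor.

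- First bullet: "Unexpected serious adverse effects that might be related to the investigational product and resulted in death or were life-threatening" go to ANSM and the REB "within a maximum of seven days from the day the sponsor learned of the event", with a further 8 days for additional information.
- Second bullet: "Other expected serious adverse effects that could be related to the investigational product, at once and within a maximum of fifteen days", again with 8 further days for additional information.

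Section 10.2 defines the two terms. "An expected SAE is an event already mentioned in the most recent version of the Investigator Brochure" or in the SmPC of an authorised product. "An unexpected SAE is an event not mentioned in or whose nature, intensity, or clinical course is not consistent with the information" in those same sources. Section 10.3 adds a reclassification rule: "any event that qualifies as expected but differs in its intensity, clinical course, or frequency will be considered as an unexpected event".

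Section 11, listing the sponsor's responsibilities, says that the sponsor must "report any suspected unexpected serious adverse events related to any of the trial treatments to the competent authority, ANSM and EMEA", and must send this information to the REB and the investigators. It does not restrict this to fatal or life-threatening events, does not mention expected events, and gives no time limit.

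**The concern.** A two-step expedited rule of this form splits one class, unexpected related reactions, by severity: the shorter limit for the fatal and life-threatening ones, the longer limit for the rest. The second bullet opens with *Other*, which fits that structure, but then names expected reactions. The rest of the unexpected class drops out of the list and a class that the first bullet never dealt with comes in.

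This is an operative instruction in a trial that combines fludarabine and busulfan conditioning, ATG and deferasirox. Followed to the letter, reactions already described in the reference safety information are expedited within 15 days, while a new kind of related reaction that leads, for example, to hospitalization or disability has no time limit for reaching ANSM or the REB.

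**Working it through.** No arithmetic applies. The check sets each class of related serious reaction against every reporting rule in Sections 10.2, 10.3 and 11.

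**Step 1: are the two classes exclusive?** On the Section 10.2 definitions alone, an event listed in the reference document but different in intensity could seem to meet both. The reclassification rule in Section 10.3 settles this: such an event counts as unexpected. No unexpected event can then enter through the second bullet.

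**Step 2: coverage as written.**

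| Related serious reaction | Deadline to ANSM/REB, Section 10.3 | Within the Section 11 duty? |
|---|---|---|
| Unexpected, fatal or life-threatening | 7 days | Yes |
| Unexpected, neither fatal nor life-threatening | none | Yes, but no time limit |
| Expected, fatal or life-threatening | 15 days | No |
| Expected, neither fatal nor life-threatening | 15 days | No |

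Under the seriousness criteria in Section 10.2, the second row holds unexpected reactions that require or prolong hospitalization, cause disability or incapacity, cause a congenital anomaly, birth defect or abortion, or are medically significant.

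**Step 3: does another rule supply the missing deadline?**

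- The investigator reports every SAE within 24 hours and sends follow-up information within 48 hours. Both go to the sponsor's side, not to the authority.
- The sponsor sends copies of all SAEs to the ATG supplier within 24 hours and to the deferasirox supplier within 15 days. Both recipients are companies, not ANSM or the REB.
- The annual safety report goes to the authority and the REB, but it is periodic and sets no deadline for a single case.
- Section 11 states the duty without a time limit.

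None of these fills the second row.

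**Step 4: the reclassification rule.** Take an expected, related serious reaction that is neither fatal nor life-threatening. It has a 15-day limit. Suppose that it proves more intense than the reference document describes, but still not life-threatening. It becomes unexpected, moves from the fourth row to the second, and loses its limit. The rule exists to treat such an event more cautiously, and with the present wording it does the opposite.

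**Step 5: coverage with *unexpected* in the second bullet.** The first row keeps 7 days, the second gains 15 days, and the third and fourth drop out of expedited reporting. The classes in Section 10.3 then match those in Section 11 row for row, and reclassification brings a deadline in instead of removing one.

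**The case against.** The strongest defence is that this is a visible drafting slip. *Other*, placed straight after a bullet on unexpected reactions, points to *unexpected*, and Section 11 points the same way, so an experienced pharmacovigilance unit may well read the clause as it was meant. Nothing in the Protocol shows that anyone has applied it literally. Reporting by the investigator to the sponsor is also intact. All of this stands, and it limits the likely harm. It does not remove the error: a unit that reads the clause sensibly departs from the written text.

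A reader might infer more than the documents support, in four ways.

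- *That all unexpected non-fatal reactions lose their deadline.* They do not. Life-threatening ones keep the 7-day rule even if the patient survives.
- *That the sponsor no longer has to report the omitted class.* It does, under Section 11. The time limit and the place in the operative list are what is lost. The conflict between the sections is one of scope, since Section 11 sets no competing deadline.
- *That the DSMB would hear of new risks late.* The Section 10.3 rule concerns ANSM and the REB. Section 12 does not make the DSMB's information depend on it.
- *That a large number of expected reactions would be sent by mistake.* The Protocol gives no rate from which to estimate this. It also keeps aplasia from conditioning, transfusions and the transplant hospitalization out of the SAE definition, and ends routine SAE reporting 30 days after transplant or last study drug.

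**Conclusion.** The second bullet is wrong as written and should be corrected. Of the four classes of related serious reaction, one that Section 11 requires to be reported has no deadline to ANSM or the REB anywhere in the Protocol, and two that lie outside the Section 11 duty carry a 15-day deadline. The conclusion rests only on the wording of Sections 10.2, 10.3 and 11, with expected and unexpected read as exclusive. How many reports would be affected cannot be derived from the Protocol, and the point does not need that number. Sample size, power, type I error and the survival comparison are untouched. The matter is the timeliness of safety reporting.

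**What to change.** In the second bullet of the authority-reporting list in Section 10.3, change *expected* to *unexpected*. The 15-day limit and the 8 further days can stay as they are. A cross-reference from the sponsor's duty in Section 11 to the deadlines in Section 10.3 would help to keep the two places aligned.

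The cost is one word in the next amendment and a note to the sponsor's pharmacovigilance unit. No additional data are collected and no analysis changes. Expected related reactions would no longer need a 15-day report under this bullet.
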